4.5.1 Extent of Exposure

Extent of exposure to study treatment will be summarized for the SAF by treatment group. The duration of exposure will be presented in days and calculated as the date of last dose of IP minus the date of first dose of IP, plus one. Duration of exposure and total dose received (mg) will be summarized using descriptive statistics.

4.5.2 Adverse Events

Treatment-emergent AEs are defined as those AEs with onset after the first dose of IP or existing events that worsened after the first dose during the study.

Treatment-emergent AEs will be summarized by treatment group through the end of Treatment Period 2. Select TEAE summaries through the end of Treatment Period 2 will also be presented by treatment period. Any AEs reported during the post treatment Follow-up period will be summarized separately by treatment sequence.

Each TEAE will be assigned to a single treatment using the date and time of onset. A TEAE that occurs after the first dose of IP in Treatment Period 1 but before the first dose of the IP in Treatment Period 2 will be assigned to the treatment associated with Treatment Period 1. This includes TEAEs that may occur in the washout interval between treatment periods.

A TEAE that continues over both treatment periods will be counted only once in the period during which the event started unless the TEAE worsens in severity, in which case the TEAE will be attributed to the treatment period during which it progressed to its most severe intensity. Events reported with a partial onset date (e.g., month and year are reported but the day is missing) will be considered to be treatment-emergent if it cannot be confirmed that the event onset was prior to the first dose of IP based on the available date entries.

Verbatim terms on case report forms will be mapped to preferred terms and system organ classes using the Medical Dictionary for Regulatory Activities (MedDRA, version 24.1).

Summaries that are displayed by system organ class and preferred terms will be ordered by descending incidence of system organ class and preferred term within each system organ class. Summaries displayed by preferred term only will be ordered by descending incidence of preferred term. Summaries of the following types will be presented:

- Overall summary of number of unique TEAEs and treatment-emergent serious adverse events (SAEs) and subject incidence of TEAEs meeting various criteria;
- Subject incidence of TEAEs by MedDRA system organ class and preferred term;
- Subject incidence of the most frequently-occurring TEAEs (i.e., TEAEs occurring in ≥ 10% of the SAF) by MedDRA preferred term;

Confidential Page 24 of 28

- Subject incidence of TEAEs by CTCAE grade, MedDRA system organ class, and preferred term;
- Subject incidence of TEAEs by relationship to IP, MedDRA system organ class, and preferred term;
- Subject incidence of the most frequently-occurring TEAEs related to IP (i.e., related TEAEs occurring in ≥ 10% of the SAF) by MedDRA preferred term;
- Subject incidence of ≥ Grade 3 TEAEs related to IP by MedDRA system organ class and preferred term;
- Subject incidence of SAEs by MedDRA system organ class and preferred term;
- Subject incidence of serious TEAEs by CTCAE grade, MedDRA system organ class, and preferred term; and
- Subject incidence of serious TEAEs by relationship to IP, MedDRA system organ class, and preferred term.

In addition, subject incidence of TEAEs by system organ class and preferred term will be summarized by treatment sequence for the washout and follow-up periods.

At each level of summarization (e.g., any AE, system organ class, and preferred term), subjects experiencing more than one TEAE will be counted only once. In the summary of TEAEs by CTCAE grade, subjects will be counted once at the highest grade reported at each level of summarization; in the summary of TEAEs by relationship, subjects will be counted once at the closest relationship to IP. Adverse event data will be presented in data listings by subject, treatment sequence, treatment group, and event.

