10.5. Investigational Product Administration

NB-001 or placebo capsules will be administered orally to the subject. Subjects will take 2 capsules BID, 2 in the morning and 2 in the evening (i.e., 4 capsules daily). The subject should begin dosing for Treatment Period 1 on the morning of Day 1, after collection of pre-dose samples. If Day 0 and Day 1 are combined, the Investigator should schedule the combined Day 0/Day 1 visit early enough in the morning to ensure all Day 0 procedures are completed, pre-dose samples collected, and the total daily dose is taken (2 capsules, BID; 4 capsules total), in that order. Similarly, the subject should begin dosing for Treatment Period 2 on the morning of Day 50 after collection of pre-dose samples. If Day 49 and Day 50 are combined, the Investigator should ensure that the procedures required for Day 49 are completed at the end of the wash-out period and prior to pre-dose sample collection and dosing.

Capsules may be either swallowed whole or, if the subject is unable to swallow a capsule whole, it may be opened, and its contents sprinkled on applesauce. If the subject can swallow the capsules intact, sufficient liquids should be taken to swallow the capsule. If dosing is delayed, the subject should take the dose as soon as remembered with a minimum of 4 hours between doses. For example, if the subject forgets to take the morning dose and takes it upon

remembering in the afternoon, the subject should wait at least 4 hours before taking his/her evening dose. Missed doses should be reported to the Investigator.

Dosing will be paused from Days 43-49, during the wash-out period. No capsules will be taken during this time. The wash-out period may be extended beyond one week (and within reason) to accommodate the subject's schedule, after consultation with the Clinical Research Associate (CRA) or Medical Monitor.

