12.2. Adverse and Serious Adverse Events

12.2.1. Definition of Adverse Events

12.2.1.1. Adverse Event

An AE is defined as any untoward medical occurrence in a clinical investigation subject administered an IP and which does not necessarily have a causal relationship with the product. An AE can therefore be any unfavorable and unintended sign (including an abnormal laboratory finding), symptom, or disease temporally associated with the use of a pharmaceutical product, whether or not it is considered related to the pharmaceutical product.

Pre-existing events that increase in frequency or severity in nature during or as a consequence of use of an IP will also be considered as AEs. Any medical condition or clinically significant laboratory abnormality with an onset date before the date of ICF signature is pre-existing and

should be documented as medical history. Any AE that occurs between the date of ICF signature and the date/time of first IP administration will be considered a pre-treatment-emergent AE. Any AE that occurs after the date/time of first IP administration will be considered a TEAE.

Often, a clinically significant laboratory value is an abnormal laboratory value that is accompanied by a sign or symptom. Typically, a diagnosis or set of clinical signs and symptoms including abnormal laboratory value(s) is captured as the AE term (e.g., anemia). However, in the absence of a diagnosis, a clinically significant laboratory abnormality may be captured as an AE term (e.g., elevated alanine aminotransferase). All laboratory values, including abnormal values, will be reported during the trial.

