4.1.2 Summarization by Visit

Data summarized by study visit will be based on the nominal, scheduled visit label as reported on the eCRF for each treatment group. Each treatment period consists of 42 days and study visits in Treatment Period 2 will be labeled according to the respective day within that treatment period. For example, the Day 63 visit occurs during Treatment Period 2 and will be labeled as Day 14 within that period. Data collected for the last subject treatment visit completed within each treatment period will be summarized separately for:

- The scheduled visit for those subjects who complete the scheduled end of treatment visit in each treatment period per protocol. This will be the scheduled Day 42 for subjects in Treatment Period 1 and Day 91 for subjects in Treatment Period 2. This summary will be labeled as "Day 42" in the analysis; and
- The last treatment visit completed on-study, combining data collected for subjects who complete the scheduled end of treatment visit, as well as the visit data for those subjects who discontinue the study early. This summary will be labeled as "Day 42/ET" in the analysis.

Data collected at unscheduled visits within the double-blind treatment period will not be included in by-visit summaries, but will be considered when endpoint derivations potentially include multiple visits (e.g., determination of baseline value, determination of worst post-baseline value, etc.). All data will be included in subject listings.

Any summarization of data collected during the follow-up period will be presented separately and will be based on the nominal, scheduled visit label as reported on the eCRF.

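### SAP 4.5.2 counts off-drug adverse events towards a treatment after Period 1 but not after Period 2, so the two sequences and the two periods are not counted alike

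*SAP*

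**What the plan says.** Protocol 12.2.1.1 sets a start for treatment-emergent events but no end: "Any AE that occurs after the date/time of first IP administration will be considered a TEAE". The end comes from the tabulation rules in SAP 4.5.2.

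- After Period 1, an event with onset between the first Period 1 dose and the first Period 2 dose belongs to the Period 1 treatment. "This includes TEAEs that may occur in the washout interval between treatment periods".
- After Period 2, the main tables close: "Treatment-emergent AEs will be summarized by treatment group through the end of Treatment Period 2". Later events go elsewhere: "Any AEs reported during the post treatment Follow-up period will be summarized separately by treatment sequence".
- Select TEAE tables are also to be shown by treatment period.
- A further table gives TEAE incidence by system organ class and preferred term, which "will be summarized by treatment sequence for the washout and follow-up periods".

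On timing, SAP 4.1.2 states: "Each treatment period consists of 42 days". Protocol 10.5 states: "Dosing will be paused from Days 43-49, during the wash-out period". It also allows a longer gap after consultation, without an upper limit: "The wash-out period may be extended beyond one week (and within reason".

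Protocol 15.5 places an event under whichever treatment the subject is on when it begins. SAP 4.7, which records changes from the protocol, says nothing about adverse event attribution.

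**The concern.** The same kind of event is handled in two ways, depending only on the order of treatments. Take an event two days after the last NB-001 dose. In A/P it falls on Day 44, inside the wash-out, and counts under NB-001. In P/A it falls on Day 93, in follow-up, and does not. Placebo shows the mirror image.

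Safety and tolerability is the primary objective, so the by-treatment TEAE table is the central table of the trial. A reader of its NB-001 column would be looking at on-drug events from both sequences mixed with off-drug events from one. The by-period tables have a related fault: Period 1 has a longer window, so a higher Period 1 incidence could be taken for a period effect when it reflects only the extra days.

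**Working it through.** **Inputs.** The schedule in Protocol Table 3 and 10.5 has dosing on Days 1 to 42 and Days 50 to 91, wash-out on Days 43 to 49, and an End of Trial Visit on Day 119. About 34 subjects are randomized 1:1 (Protocol 6.2 and 6.3), taken here as 17 per sequence. Day 91 is taken as the end of Period 2, because the SAP does not define it further.

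**Step 1: the stated period length.** Period 1 is 42 − 1 + 1 = 42 days and Period 2 is 91 − 50 + 1 = 42 days, which agrees with SAP 4.1.2. Wash-out is 49 − 43 + 1 = 7 days. Follow-up is 119 − 91 = 28 days.

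**Step 2: attribution windows under SAP 4.5.2.** Period 1 is 42 + 7 = 49 days and Period 2 is 42 days, a ratio of 49/42 = 1.17. If the wash-out were extended by one week (an assumption), the ratio would be 56/42 = 1.33.

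| | A/P | P/A |
|---|---|---|
| NB-001 window | 49 days | 42 days |
| Placebo window | 42 days | 49 days |

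**Step 3: does either treatment gain overall?** With full completion, NB-001 has 17 × 49 + 17 × 42 = 1,547 subject-days, and placebo has 17 × 42 + 17 × 49 = 1,547. With an assumed 18/16 split the totals are 18 × 49 + 16 × 42 = 1,554 and 18 × 42 + 16 × 49 = 1,540, a difference of 0.9%. With 20/14 they are 1,568 and 1,526, or 2.8%.

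**Step 4: which off-drug events reach the NB-001 column?** Let q be the assumed probability of an event in the 7 days after the last NB-001 dose. The expected number of subjects with such an event counted under NB-001 is 17q under the SAP and 34q under a rule with a 7-day tail in both periods.

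| q | SAP | Equal tail |
|---|---|---|
| 5% | 0.85 | 1.7 |
| 10% | 1.7 | 3.4 |
| 20% | 3.4 | 6.8 |

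The SAP takes half of them, whatever q is.

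**Step 5: by-period tables.** With an assumed constant event rate λ per day, the same on and off drug, subject incidence over d days is 1 − exp(−λd).

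| λ | 42 days | 49 days |
|---|---|---|
| 0.005 | 18.9% | 21.7% |
| 0.01 | 34.3% | 38.7% |
| 0.02 | 56.8% | 62.5% |

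Period 1 would appear about 3 to 6 percentage points worse with no true difference. These figures compare periods, not treatments, and the rates have no source in the documents.

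**The case against.** A reader might infer that events after NB-001 are lost, or that the rule tilts the comparison between treatments. The documents support neither.

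- **Events are not lost.** The by-sequence table covers both wash-out and follow-up. With two sequences, sequence plus interval identifies the last treatment, so A/P wash-out can be set beside P/A follow-up by hand. Listings carry sequence and treatment, and deaths, serious events and events of special interest are listed separately. This stands. However, the two intervals differ in length (7 against 28 days), and the by-sequence table is specified only by system organ class and preferred term, not by grade or relationship.
- **The endpoint concerns time on NB-001.** Protocol 5.1.1 and 5.2.1 frame safety as findings while on treatment, so leaving off-drug P/A events out of the NB-001 column is not a gap in the endpoint. This also stands. It means that including the wash-out events is the step away from the protocol.
- **No treatment bias is shown.** Attributed time is equal under 1:1 completion and nearly equal under modest imbalance. Within a period, both treatments have the same nominal window. A dropout between periods removes a whole 42-day period from one treatment, which far outweighs a 7-day tail under any rule.
- **The practical size may be small.** Protocol 4.3.1 gives a half-life of about 4 hours in healthy adult males, so five half-lives is about 20 hours. The documents give no rate for delayed or discontinuation events.

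One could also cite an earlier sentence of Protocol 15.5, which maps events by comparing onset with the first dose in each period. Read alone, it would keep wash-out events with Period 1. But it would equally keep follow-up events with Period 2, which the SAP does not do, and the later sentence of 15.5 refers to the treatment in use at onset.

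**Conclusion.** The inconsistency is explicit in SAP 4.5.2. The nominal windows are 49 and 42 days, off-drug events after NB-001 count under NB-001 in one sequence only, and the by-period summaries are not comparable. The wash-out rule departs from Protocol 15.5 without an entry in SAP 4.7.

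The conclusion goes no further. Attributed time is 1,547 subject-days for each treatment if 34 subjects split evenly and all complete, and the P/A follow-up events are still reported by sequence. The window lengths follow from the schedule. The incidence and subject counts above rest on assumed rates and only illustrate scale. This is a definition to put right before unblinding, not a threat to the comparison of NB-001 with placebo.

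**What to change.** In SAP 4.5.2, use one attribution rule of equal length for both periods.

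**Closest to Protocol 15.5.** Attribute an event to a treatment only if onset falls from the first to the last dose of that period, which gives 42 and 42 days. Show off-drug events in a separate table by last treatment taken, over an equal post-dose window:

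- NB-001: A/P wash-out together with the first 7 days of P/A follow-up;
- placebo: P/A wash-out together with the first 7 days of A/P follow-up.

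End each window early at the first dose of the next product, whether Period 2 or open-label extension. Report events beyond 7 days, including those in an extended wash-out, separately.

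**Alternative.** A strict last-dose cut moves an event on the morning after the last dose to the off-drug table. If the sponsor prefers a post-dose tail in the main tables, apply the same tail to both periods and record the departure from Protocol 15.5 in SAP 4.7. Seven days matches the nominal wash-out (49 and 49 days) but is one choice among several.

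Under either option, define the end of Treatment Period 2, and state which rule covers a subject who stops in Period 1 and never takes a Period 2 dose.

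**Cost.** SAP wording and minor reprogramming. No new data are needed, since adverse events are recorded through the End of Trial Visit. Extension entrants, for whom Protocol 8.5 waives the Day 119 visit, may have a shorter window after Period 2. Because entry depends on perceived benefit, that shortening is selective and should be footnoted.

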4.5.3 Deaths, Other Serious Adverse Events, and Other Significant Adverse Events

All deaths during the study, including the post treatment follow-up period, will be listed by subject, to include the primary cause of death. Serious AEs and other significant AEs, including those that led to withdrawal, interruption, or dose reduction of the IP, will be provided in separate subject data listings.

Treatment-emergent AE-SIs in this trial will include the development of psychotic symptoms, SIB, seizure, overdose with untoward medical sequalae, and confirmed cases of COVID-19, and will be provided in a subject data listing.

4.5.4 Clinical Laboratory Evaluation

All descriptive summaries of laboratory results will be based on data analyzed by the central laboratory and presented in Système International (SI) units, as suggested by the Center for Biologics Evaluation and Research and the Center for Drug Evaluation and Research *Position on Use of SI Units for Lab Tests* (Oct 2013). Summaries will also be presented in conventional units. All data will be included in by-subject data listings. Laboratory measurements identified as abnormal (i.e., outside the normal range) will also be listed separately by subject, laboratory test, and unit. In addition, normal ranges provided by the central laboratory will be presented in a separate listing.

Confidential Page 25 of 28

Clinical laboratory measurements, including serum chemistry and hematology, will be summarized by treatment group. Descriptive statistics will be presented for observed values and changes from baseline at each visit where parameters were scheduled to be collected per the clinical study protocol.

Where applicable, laboratory results will be classified as "low," "normal," or "high" with respect to the parameter-specific reference ranges (i.e., below the lower limit of the normal range, within the normal range, or above the upper limit of the normal range). Three-by-three contingency tables will be presented for each laboratory parameter to summarize the shift from the baseline category to the worst post-baseline measurement, defined as the value numerically farthest outside of the normal range across all post-baseline visits through the end of the study.

Summary results will include the count and percentage of subjects within each shift category and treatment group.

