7. SELECTION AND WITHDRAWAL OF SUBJECTS

7.1. Subject Inclusion Criteria

Subjects must meet all of the following subject inclusion criteria to be eligible to participate in the trial:

- 1. The subject has a genotype with a pathologic deletion in the 22q11 region confirmed by documentation (e.g., genetic test results) available at the clinical trial site.
- 2. The subject is aged 6 to 17 years old, inclusive.
- 3. The subject has a CGI-S scale score of ≥4 (i.e., moderately, markedly, severely, or among the most extremely ill patients) at Screening. Note that the Severity score of 4 could be from a composite of 2 or more sub-threshold scores.

And either:

- a. Psychiatric symptoms in the clinical range for **at least 1 of 3 disorders**, anxiety disorder, ADHD, or ASD, respectively, as demonstrated by score(s) at or above the following numbers *on at least 1 of 3 scales*:
 - PARS 5-Item Severity Score ≥ 12 (i.e., sum of items $2+3+5+6+7 \geq 12$)
 - ADHD-RS-5 Scores of 2 or 3 (i.e., "Often" or "Very Often") on at least 6 questions, with the majority of symptoms related to inattention (common in 22q11DS) rather than hyperactivity (less common in 22q11DS)
 SRSTM-2 >60

• SF

OR:

- b. Psychiatric symptoms in the **subclinical range for at least 2 of 3 disorders**, anxiety disorder, ADHD, and/or ASD, respectively, as demonstrated by scores at or above the following numbers *on at least 2 of 3 scales*:
 - PARS 5-Item Severity Score of 10 or 11 (i.e., sum of items 2+3+5+6+7=10 or 11)
 - ADHD-RS-5 Scores of 2 or 3 (i.e., "Often" or "Very Often") on 4 or 5 questions, with the majority of symptoms related to inattention (common in 22q11DS) rather than hyperactivity (less common in 22q11DS)
 - SRSTM-2 of 55-59
- 4. The subject has adequate renal and hepatic function indicated by:
 - Estimated glomerular filtration rate (eGFR) ≥60 mL/min/1.73 m² (per the revised Schwartz equation; Fadrowski and Furth 2011; Staples et al. 2010)
 - serum bilirubin ≤2.5 × upper limit of normal (ULN), unless documented Gilbert's Disease; aspartate aminotransferase and alanine aminotransferase ≤2.5 × ULN
- 5. If the subject is female and of reproductive potential, she has a negative serum pregnancy test at Screening and a negative urine pregnancy test on Day 0.
- 6. If the subject is of reproductive potential, s/he agrees to abstain from reproductive cell donation, per below, and, if ever heterosexually active, to use dual effective/highly

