Other laboratory tests may be performed by the Investigator, as deemed necessary, to evaluate, or ensure the safety of, a subject. The performance of special testing (i.e., other than the protocol-defined testing) that the Investigator deems necessary should be discussed in advance with the Medical Monitor, if the subject's clinical status allows.

A blood sample to assess serum proline levels will be collected as described in Table 3. There is evidence that proline affects glutamatergic neurotransmission. PRODH, a protein coding gene, encodes the enzyme proline dehydrogenase, which is involved in the transformation of the amino-acid proline into pyrroline-5-carboxylate, which in turn is the precursor of glutamate. In a subset of patients with 22q11DS, plasma proline levels are found to be increased (Goodman et al. 2000). Variability in proline levels in 22q11DS is likely related to polymorphisms in the remaining allele of the PRODH gene (Bender et al. 2005). In 22q11DS, several studies indicate a

possible relation between high proline and changes in neuropsychiatric phenotypes (Raux et al. 2007; Vorstman et al. 2009; Magnee et al. 2011) but this observation is not consistently replicated (Evers et al. 2015).

If any blood remains from the sample collected for centralized confirmation of 22q11DS genotype, the remnant blood samples will be stored per the federal (and/or local) regulations that govern the laboratory's processes on biological sample (and laboratory report) retention. Additionally, if a new protocol and informed consent form are developed to investigate the remnant samples, these documents will be submitted for IRB and/or EC approval and the subject and/or parent/guardian will be required to provide documented informed consent for additional analyses of the samples. Table 3. At the time of signing the initial ICF for this trial, NB-001-01, the subject and/or parent/guardian will have the option to decline future research on any remnant blood sample.

Blood samples for PK analysis and 4β -hydroxycholesterol will be collected at the timepoints noted in Table 3.

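### The laboratory shift tables stop at high, so a child whose ALT, AST or bilirubin is already above ULN at a period's baseline cannot register worsening in them

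*SAP*

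**What the plan says.** SAP section 4.5.4 sets the categories: "laboratory results will be classified as 'low,' 'normal,' or 'high' with respect to the parameter-specific reference ranges". It then says: "Three-by-three contingency tables will be presented for each laboratory parameter to summarize the shift from the baseline category to the worst post-baseline measurement". The worst measurement is "defined as the value numerically farthest outside of the normal range across all post-baseline visits through the end of the study". Counts and percentages are given for each shift category within each treatment group.

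Protocol section 7.1, criterion 4, admits children with "aspartate aminotransferase and alanine aminotransferase ≤2.5 × ULN" and "serum bilirubin ≤2.5 × upper limit of normal (ULN), unless documented Gilbert's Disease".

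Under SAP section 4.5 the safety baseline is the last value before the first dose of each treatment period. Protocol section 5.2.1 makes clinically significant laboratory changes part of the primary endpoint. The SAP applies CTCAE grades to adverse events but not to laboratory values. It plans no bands by multiple of ULN and no summary by multiple of baseline.

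**The concern.** The shift table is cut at the edges of the normal range, while the protocol knowingly admits values above the upper edge. For a child already above it there is no higher category to move into. The rule for choosing the worst value uses distance outside the range, but the table then discards that distance.

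At stake is the count by treatment. If NB-001 raised transaminases or bilirubin further in children with raised baselines, the one categorical laboratory table that compares NB-001 with placebo would look the same as if nothing had happened to them.

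**Working it through.** The plan gives no figure to reproduce. The check is whether the classification rule can show a rise.

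**Inputs.** Category rule: high if the value exceeds 1 × ULN (SAP 4.5.4). Admissible entry range above normal: more than 1 and up to 2.5 × ULN (Protocol 7.1). Baseline: last pre-dose value in the period (SAP 4.5).

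**Step 1: enumerate.** Baselines from just above 1 to 2.5 × ULN were crossed with rises of up to 20-fold, and each pair was classed by the SAP rule. The share leaving the high-to-high cell was 0%. In the examples below, the right-hand column uses illustrative bands (≤1, >1–2.5, >2.5–5, >5–10, >10 × ULN). These bands are an assumption, not taken from the documents.

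| Baseline × ULN | Fold rise | Worst × ULN | SAP 3×3 table | Banded table |
|---|---|---|---|---|
| 0.8 | 1.5 | 1.2 | normal to high | ≤1 to >1–2.5 |
| 1.0 | 5 | 5.0 | normal to high | ≤1 to >2.5–5 |
| 1.1 | 2 | 2.2 | high to high | stays in >1–2.5 |
| 1.1 | 5 | 5.5 | high to high | >1–2.5 to >5–10 |
| 1.5 | 5 | 7.5 | high to high | >1–2.5 to >5–10 |
| 2.5 | 2 | 5.0 | high to high | >1–2.5 to >2.5–5 |
| 2.5 | 5 | 12.5 | high to high | >1–2.5 to >10 |

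The first two rows share one cell of the SAP table although the rises differ greatly. The third row shows that bands alone still miss a doubling within a band.

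**Step 2: where else the rise would show.** SAP 4.5.4 gives observed values and changes from baseline at scheduled visits, and SAP 4.1.1 includes SD, quartiles and maximum. The mean itself moves little. Take one child rising from a hypothetical 2.4 to 7.2 × ULN. The group mean change shifts by (7.2 − 2.4)/34 = 0.14 × ULN with about 34 children in the safety set, or 4.8/30 = 0.16 with 30.

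SAP 4.1.2 keeps values from unscheduled visits out of by-visit summaries but lets them count towards the worst post-baseline value. Protocol 12.1.5 schedules one on-treatment draw per period (Day 42 and Day 91/ET). For a child with a raised baseline, a peak at an unscheduled draw therefore enters only the shift table, where it reads high to high. Beyond that it appears in the listings, and among TEAEs if it is recorded as one.

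**Step 3: how many children.** The documents give no share with a baseline above ULN. The 2.5 × ULN limit is a ceiling, not a prevalence. As an assumption only, 0%, 5% and 20% of 34 give 0, 1.7 and 6.8 children. A period baseline can also become raised after entry: no laboratory sample is scheduled in the wash-out, so the Period 2 baseline will usually be Day 42, the last dosing day of Period 1.

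**The case against.** The SAP is internally consistent here. It defines its categories and pairs the shift table with other outputs. Under Protocol 12.1.5 the investigator assesses every out-of-range value for clinical significance. Protocol 12.2.1.1 gives raised ALT as an example of an abnormality that may be an AE term, and it counts worsening of a pre-existing event as an AE. SAP 4.5.2 tabulates TEAEs by treatment and CTCAE grade. The spread and maximum of the changes would expose a large outlier in so small a trial, and abnormal values are listed separately. All of this stands. It means the gap lies in one table, not in the whole safety report. The TEAE route, however, depends on a case-by-case judgement, whereas the shift table is meant to count values without one.

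Four stronger readings are tempting, and the documents do not support them:

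- *Every child admitted above ULN is affected under both treatments.* Eligibility is established at Screening, while the baseline is the last pre-dose value of each period. A child high at Screening but normal at Day 0 would still register normal to high.
- *The rise disappears from the report.* It does not, for the reasons just given.
- *These children are the ones most exposed to liver effects.* Nothing in the visible text says so. Protocol 4.3.1 names renal clearance as the main elimination route, and the events of special interest include no hepatic term.
- *Local-laboratory values are left out.* SAP 4.5.4 says "All descriptive summaries of laboratory results will be based on data analyzed by the central laboratory", and Protocol 12.1.5 says "Other laboratory tests may be performed by the Investigator, as deemed necessary, to evaluate, or ensure the safety of, a subject". Neither document says that such tests would be run locally or would be liver tests, and all data are listed in any case.

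**Conclusion.** The point holds as a limit of one table. For any child whose period baseline for ALT, AST or bilirubin is above ULN, none of the upward changes tested can appear as a shift, under NB-001 or placebo. This follows from the category rule and needs no distributional assumption. Its practical size is unknown: the number of such children is not stated and may be zero, and the counts of 1.7 to 6.8 rest on an assumed 5% to 20%. This is a low-cost improvement to the tabulation of part of the primary endpoint, not an error that invalidates the safety analysis.

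**What to change.** In SAP section 4.5.4, for ALT, AST and total bilirubin, replace or supplement the three-by-three table with two displays by treatment group:

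1. Baseline band against worst (highest) on-treatment band within the period, using ordered multiples of ULN with one cut at the protocol's own 2.5 × ULN (for example ≤1, >1–2.5, >2.5–5, >5–10, >10), or CTCAE v5.0 grades, which the trial already applies to adverse events.
2. A count of children by highest on-treatment value as a multiple of their period baseline (for example cut at 1.5, 2, 3 and 5 times). This shows rises within a band such as 1.1 to 2.2 × ULN. It also covers bilirubin in Gilbert's Disease, where a child may start in the top band.

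These are tabulation bands only and imply no rule for patient care. The cost is SAP wording and new table shells for three parameters, using data already collected. The downside is a larger, sparser table. The change should be made before unblinding so that the cuts are not chosen after seeing the data.
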